2.1 Assessment and Management of Risk

There are some unavoidable burdens and risks to participants that will be explained fully in the Participant Information Sheet and prior to receiving informed consent to partake in the study. There is first the burden of time required from the patient, which is approximately 30 minutes additional to their standard anorectal physiology appointment time. To minimise this burden, the additional barostat test will be performed at the same time as their standard care appointment, to avoid additional travel costs and time. The barostat test also carries a risk of pain, discomfort, bleeding, and perforation of the rectum (<1 in 1000), the same as standard rectal sensitivity testing using the elastic balloon, which the patients will also be undergoing as part of their standard anorectal physiology appointment. To minimise pain and discomfort, lubrication is used to insert the catheter and the participant advised they can withdraw their consent at any point, and the test will be abandoned. To minimise the risk of bleeding, the test will be abandoned if there is any resistance during insertion of the catheter and participants are excluded from the study if they suffer from excessive or unexplained rectal bleeding. Any participants with risk factors of rectal perforation, such as previous pelvic surgery, pelvic radiotherapy, or inflammatory bowel disease are excluded from the study (according to exclusion criteria), and the barostat automatically deflates if pressure of the rectal wall exceeds 40 mmHg.

This trial is categorised as Type A (no higher than the risk of standard medical care).

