CI – Chief Investigator

CRF – Case Report Form

CTIMP - Clinical Trial of an Investigational Medicinal Product

GCP – Good Clinical Practice

GI – Gastrointestinal

IBS – Irritable Bowel Syndrome

IBS-C – Irritable Bowel Syndrome Constipation Subtype

MRN - Medical Record Number

NUTH – Newcastle Upon Tyne Hospitals

PCF – Participant Consent Form

PI – Principle Investigator

PIS – Patient Information Sheet

QA – Quality Assurance

REC – Research Ethics Committee

SAE - Serious Adverse Event

STP – Scientist Training Programme

UEG – United European Gastroenterology

R&D Ref: 10618 IRAS ID: 331715

STUDY SUMMARY

Study Title	A feasibility study to assess rectal sensitivity using elastic balloon distension versus a rapid rectal barostat bag: is there an agreement in London classification diagnoses?	
Short Trial	Assessing rectal sensitivity with elastic balloon versus rectal barostat	
Study Design	Feasibility study, Non-CTIMP, Randomised Multi-site study	
Study Participants	Inclusion criteria: Aged over 18 years Aged under 90 years Male or nonpregnant female Meets 1 or more of the following indications for anorectal physiology investigations: symptoms of constipation or disorder of evacuation, faecal incontinence, functional anorectal pain, faecal urgency and frequency of moving bowels, constant urge to move bowels. Has had a previous lower gastrointestinal tract investigation (colonoscopy, flexible sigmoidoscopy, defecating proctogram, digital rectal examination, CT colon) in the past 2 years Able to understand written and verbal English Exclusion criteria: Creutzfeldt-Jakob disease Pregnancy Previous rectal surgery Previous pelvic radiotherapy Haemorrhoid banding in past 2 weeks Haemorrhoidectomy in past 10 weeks Reporting of change of bowel habits, rectal bleeding, or weight loss with no endoscopic investigations performed since symptoms commenced History of inflammatory bowel disease History of colorectal or anal cancer Lack of capacity to consent Over 90 years old Under 18 years old Currently or has been involved in a clinical trial investigational medicinal product study within 6 months prior to the start of the study. Unable to understand written and/or verbal English	

Planned Sample Size	30	
Planned Study Period	24 months	
	Objectives	Outcome Measures

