6.2 Exclusion Criteria

- Creutzfeldt-Jakob disease
- Pregnancy
- Previous rectal surgery
- Previous pelvic radiotherapy
- Haemorrhoid banding in past 2 weeks
- Haemorrhoidectomy in past 10 weeks
- Reporting of change of bowel habits, rectal bleeding, or weight loss with no endoscopic investigations performed since symptoms commenced
- History of inflammatory bowel disease
- History of colorectal or anal cancer
- Lack of capacity to consent
- Over 90 years old
- Under 18 years old

12 of 21

Study protocol: Assessing rectal sensitivity with elastic balloon distension versus rectal barostat.

- Currently or has been involved in a clinical trial investigational medicinal product study within 6 months prior to the start of the study
- Unable to understand written and/or verbal English

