7.0 STUDY PROCEDURES

7.1 Recruitment

Referrals from Consultant Gastroenterologists or Colorectal Surgeons to the GI Physiology Service at NUTH or CDDFT for anorectal physiology studies will be screened for study eligibility, according to the inclusion and exclusion criteria. This will be performed by trained healthcare scientists or a trainee clinical scientist (NHS STP) under supervision. The team performing the screening and all study procedures are the same individuals that would usually be involved in the standard care of the patient.

During standard care a standard anorectal physiology patient information leaflet (PIL) and appointment letter is sent to the patient. The standard appointment letter states that the patient can call the GI physiology secretary to make an appointment for their standard anorectal physiology test or the patient can be called by the GI physiology secretary to make an appointment.

As part of the research study eligible patients will also be sent a study patient information sheet (PIS) alongside the standard anorectal physiology PIL and appointment letter. The patient will then receive a telephone call from an investigator of the research team (GI physiology team), a minimum of 5 days following postage, to determine whether they would like to participate in the study. If they are willing to participate an appointment will be made, which will include their standard clinic appointment. Full eligibility will be assessed once informed consent has been given at their clinic appointment. For patients who do not want to participate they will continue with standard care and a standard anorectal physiology appointment will be made.

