7.2.2 Participant Identification Log

Participants recruited to the study will be documented within the participant identification log, which will include the following information:

- Participant name
- Participant initials
- Screening number
- Subject number
- NHS number
- MRN (medical record number)
- Confirmation of eligibility
- Date of consent
- Personal details (address, phone number, email address)
- Withdrawal (yes, no/when and why)

The researcher will use a checklist to determine clinical eligibility. If recruited, patients will be assigned a Case Report Form (CRF).

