7.5.4 Rectal Barostat

Participants from NUTH and CDDFT will have the rectal barostat test performed as per local procedure as part of non-standard care.

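### Section 2.1 says patients with previous pelvic surgery are excluded as a perforation risk, but Section 6.2 and the study summary exclude only previous rectal surgery

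*Protocol*

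**What the plan says.** Section 2.1 of the protocol describes how the risks of the added barostat test are controlled. It puts the risk of "perforation of the rectum (<1 in 1000), the same as standard rectal sensitivity testing using the elastic balloon". Among the mitigations it states that "Any participants with risk factors of rectal perforation, such as previous pelvic surgery, pelvic radiotherapy, or inflammatory bowel disease are excluded from the study", and a parenthesis in the same sentence gives the exclusion criteria as the source.

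The formal criteria appear twice. Section 6.2 has "Previous rectal surgery" as its surgical exclusion. The study summary carries the same wording: "Previous rectal surgery Previous pelvic radiotherapy Haemorrhoid banding in past 2 weeks Haemorrhoidectomy in past 10 weeks".

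Section 7.1 says that referrals "will be screened for study eligibility, according to the inclusion and exclusion criteria", with full eligibility assessed in clinic after consent. Section 7.2.2 adds: "The researcher will use a checklist to determine clinical eligibility". The checklist is not reproduced in the protocol.

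Enrolled patients at both sites "will have the rectal barostat test performed as per local procedure as part of non-standard care" (Section 7.5.4). Section 7.5.3 adds two further rounds of rectal sensitivity testing, also outside standard care.

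On bleeding, Section 2.1 says that "participants are excluded from the study if they suffer from excessive or unexplained rectal bleeding". Section 6.2 excludes rectal bleeding only where no endoscopic investigation has followed the onset of symptoms.

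**The concern.** Section 2.1 makes a statement about the protocol's own exclusion list that can be checked, and for one of its three named risk factors the statement is not true. Pelvic surgery is a wider category than rectal surgery: it includes, for example, gynaecological, bladder and prostate operations. Section 6.2 uses *rectal* for surgery and *pelvic* for radiotherapy on adjacent lines, so a screener has good reason to read the two words as different.

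What is at stake is participant safety and the accuracy of the risk account given to the ethics committee and sponsor. The exclusion is one of the protections that 2.1 offers against perforation, in the section that ends by classing the trial as no riskier than standard care. The criteria that decide who enters do not deliver that protection. The people affected would have research distensions that they would not have had outside the study.

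There is a smaller consequence for the feasibility results. The number of eligible patients is itself an outcome (Section 3.3), and two sites screen. If staff at one site apply the wording of 2.1 and staff at the other apply 6.2, the eligible counts will not mean the same thing.

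**Working it through.** No arithmetic applies. The check sets the risk section beside the operative criteria.

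| Perforation risk factor named in 2.1 | In Section 6.2? | In the study summary? |
|---|---|---|
| Pelvic radiotherapy | Yes | Yes |
| Inflammatory bowel disease | Yes | Yes |
| Previous pelvic surgery | No; rectal surgery only | No; rectal surgery only |

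Two of the three are present and one is missing.

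**Could another criterion close the gap?** The remaining criteria that relate to procedures or bowel disease are haemorrhoid banding within 2 weeks, haemorrhoidectomy within 10 weeks, and a history of colorectal or anal cancer. None covers an operation in the pelvis that left the rectum untouched. There is no general exclusion for perforation risk and no exclusion at the investigator's discretion.

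**Which wording operates?** Section 7.1 ties screening to the inclusion and exclusion criteria, and 2.1 itself defers to them. Randomisation follows confirmation of eligibility (Section 7.4). On the text shown, the narrower wording decides who enters.

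**What added exposure follows?** One barostat procedure (7.5.4) and two extra rounds of rectal sensitivity testing (7.5.3), all outside standard care. The number of barostat distensions is not stated. Section 7.8 plans an intraclass correlation for the repeatability of the barostat thresholds, which requires more than one measurement per participant.

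**Can the added risk be sized?** No. The only figure is the bound of less than 1 in 1000. It is a general figure for the test, given in a section that describes patients with risk factors as excluded. The protocol gives no rate for patients with previous pelvic surgery and does not say how many referrals have had it.

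**Bleeding.** Section 2.1 names two kinds, excessive and unexplained. The criterion in 6.2 largely covers unexplained bleeding, since it excludes bleeding that has not been investigated by endoscopy since it began. It does not cover excessive bleeding that has been investigated, and *excessive* is nowhere defined.

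**The case against.** The strongest answer is that 2.1 is a loose paraphrase and 6.2 governs. The two formal lists agree with each other, and 2.1 points to them. Section 2.1 also rates the barostat's risk as equal to that of the elastic balloon test, which these patients would have in routine care whether or not they enrolled. Other safeguards remain: the test is abandoned on resistance, the barostat deflates above 40 mmHg, and a digital rectal examination comes first. No endpoint or analysis depends on the wording. The in-clinic eligibility check and the checklist may already apply the wider exclusion.

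Much of this stands, and it limits the point to the added research exposure and to a text correction. It does not remove the point. If 6.2 governs, 2.1 claims a protection that does not exist, and it does so for a factor that the protocol itself calls a risk for perforation. An equal average risk for the two tests does not justify extra distensions in a group that 2.1 says should have none in the study.

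Three stronger readings are tempting and are not supported.

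- A reader might infer that the sponsor meant to exclude all pelvic surgery and that 6.2 is the mistake. The documents do not settle which wording was intended.
- A reader might multiply the bound of 1 in 1000 by the 30 participants, either to show that the danger is trivial or to put a number on it. That would assume one test per participant, when 7.5.3 and 7.8 imply more. The protocol does not say whether the bound is per distension or per procedure. Recruitment continues until 15 complete data sets exist at each site (Section 6.3), so more than 30 people may be exposed. Above all, the bound is not specific to patients with pelvic surgery.
- A reader might treat the bleeding wording as an equal contradiction. It is weaker: the bleeding sentence in 2.1 does not cite the exclusion criteria, and the mismatch rests on one undefined word.

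**Conclusion.** The inconsistency is real and should be corrected. Section 2.1 says that patients with previous pelvic surgery are excluded under the criteria; Section 6.2 and the study summary exclude only rectal surgery, and no other criterion fills the gap. Followed as written, the protocol can enrol patients whom its own risk section describes as protected, and give them distensions outside standard care.

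Its size in the text is one named risk factor out of three. Its size in harm cannot be stated from the documents. The conclusion assumes that screening follows the printed criteria, as 7.1 says. The checklist in 7.2.2 is not shown, so it is not established that such patients would be enrolled in practice. A reader might also infer that the low-risk classification in 2.1 is wrong. The documents do not show that; they show only that one of the mitigations described beside it is not in the criteria.

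The bleeding mismatch is secondary and minor.

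**What to change.** Decide which wording is intended, then make Section 2.1, Section 6.2, the study summary and the eligibility checklist agree.

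- **If pelvic surgery is meant:** add *previous pelvic surgery* to 6.2, the study summary and the checklist, and list the operations that count so that both sites screen alike. Somewhat fewer referrals would qualify, by a number that the documents do not allow to be estimated.
- **If only rectal surgery is meant:** change 2.1 to *previous rectal surgery*, so that it no longer claims a protection the criteria do not give, and add a short justification for accepting patients with other pelvic surgery. This does not affect recruitment.

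In the same amendment, align the bleeding wording. Either limit 2.1 to bleeding that has not been investigated by endoscopy since it began, or add to 6.2 a criterion for excessive bleeding with a definition that screeners can apply.

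The cost is a text amendment. Under Section 11.2 every amendment needs review by the study team and approval by the sponsor; a change in eligibility also needs ethics committee approval if it is classed as major. No extra procedures or data are required.

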3.0 OBJECTIVES AND OUTCOME MEASUREMENTS/ENDPOINTS

3.1 Primary Objective

To assess the feasibility of a definitive study which will compare two different measurement methods of rectal sensitivity. These measurement methods include the gold standard rectal barostat test and the more widely used elastic balloon distension test.

10 of 21

Study protocol: Assessing rectal sensitivity with elastic balloon distension versus rectal barostat.

3.2 Secondary Objectives

- To assess whether they are any differences in rectal sensitivity diagnoses when using the London classification between the two methodologies (elastic balloon distension test and rectal Barostat test).
- To assess the repeatability of the rectal barostat test.
- To investigate whether patients with larger rectums require the elastic balloon to be inflated to a larger volume, before they feel an urge to defecate.
- To determine whether the Laborie elastic balloon test or Medtronic elastic balloon test aligns better with the rectal barostat test.
- To assess study participant eligibility, uptake and drop-out rate.
- To assess study acceptability and tolerability.
- To assess the costs per study of the two methodologies to help inform a definitive study (clinic time, analysis time and consumables).

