The most common assessment of rectal sensitivity in a clinical environment is made by gradually inflating an elastic balloon within the rectum, and measuring the volumes at which the patient reports their first sensation, their normal urge to defecate, and sustained urgency^[7]. This is commonly performed in conjunction to anorectal manometry (ARM), which involves insertion of a catheter into the anorectum, and measuring pressure at rest and during specific manoeuvres to assess the function of the anal sphincters^[8]. Most commercially available catheters for this test also contain the required elastic balloon to assess rectal sensitivities, which can be inflated manually or automatically by the equipment, depending on the model and the manufacturer. The advantages of assessing rectal sensitivities using the elastic balloon in conjunction with ARM is that it is fast and cheap, as it does not require a separate catheter being inserted for the additional test. However, the elastic properties of the balloon mean it is unsuitable to assess rectal compliance^[9]. In our

Study protocol: Assessing rectal sensitivity with elastic balloon distension versus rectal barostat.

services, we use two anorectal manometry systems across NUTH and CDDFT services. In NUTH we use a Laborie Solar High Resolution Manometry System with water-perfused catheters, and in CDDFT we use a Medtronic 3D Solid-State High Resolution Manometry System. Both systems are commercially available across the UK, and use a similar elastic balloon for inflation, however, they utilise different published normal ranges of sensory thresholds.

The rectal barostat is another, more comprehensive, device used to assess rectal sensitivity. It contains a polyethylene bag, which is inserted into the patient's rectum and inflated using a pneumatic pump either continuously or in phasic intervals^[10]. Unlike the elastic balloon, the rectal barostat bag has infinite compliance whilst filling, which allows measurement of rectal compliance and total rectal volume, due to its ability to measure opposing pressure of the rectal wall. This protocol is more time-consuming, and for this reason is not routinely used in clinical practice, however it is considered the gold-standard of assessing sensory thresholds, and has the advantage of adding additional information about the biomechanical properties of the rectal wall^[3].

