2.0 RATIONALE

A recent service evaluation was conducted to compare the number of diagnoses of disorders of rectal sensitivity (n=70 per site) across NUTH and CDDFT services, in order to identify whether both pieces of equipment produce similar proportions. In NUTH, the majority of patients (91.4%) were diagnosed as normal, whereas in CDDFT, the majority of patients (65.7%) were diagnosed with rectal hypersensitivity. This suggests a possible difference in how each piece of equipment classifies patients, although the limitations such as two different cohorts of patients being studied, and the relatively small sample size should be acknowledged. This service evaluation supported the need for more research into our normal values and how we assess rectal sensitivity, and questioned whether a rectal barostat could be more appropriate.

There is little research directly comparing the assessment of rectal sensitivity using elastic balloon distension and the rectal barostat. A study by Sauter et al. (2014) assessed 26 healthy volunteers using both the elastic balloon inflation and barostat methodologies to assess rectal sensitivities, by recording volume inflated at first sensation, normal urge, and

sustained urgency. They found there was no agreement between the elastic balloon and barostat recorded volumes, however, this is possibly due to the difference in physical properties and shape at identical volumes, which the study failed to take into account^[12]. There are currently no studies comparing the two devices in a symptomatic population, and no indication whether patients receive different diagnoses depending on what device is used to assess rectal sensitivity. Accurate and comprehensive assessment of disorders of rectal sensation to distension in symptomatic patients is vital, as studies have suggested patients with rectal hyposensitivity treated with biofeedback therapy improved their sensory thresholds and symptom severity^[14], and sensory retraining is of greater utility when treating faecal incontinence than strength training alone^[15].

This feasibility study will help investigate key variables required to inform a future definitive study, which will aim to determine whether patients receive a different diagnosis of rectal sensitivity dependent upon the test used. Moreover, a definitive study will address the potential impact of rectal sensitivity testing methodologies on patient outcomes.

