5.0 STUDY SETTING

Multicentre study. Research sites include:

- Newcastle Upon Tyne Hospitals NHS Foundation Trust (NUTH): Royal Victoria Infirmary, Medical Physics.
- County Durham and Darlington NHS Foundation Trust (CDDFT): University Hospital of North Durham, Medical Physics.

Patients identified at each site will undergo the study at the same site. Therefore, patients are not expected to travel between sites.

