7.5.3 Anorectal Manometry and Rectal Sensitivity Testing

Participants from NUTH will have anorectal manometry and rectal sensitivity tests as per local procedure using a Laborie Solar High Resolution Manometry System with water-perfused catheters. Participants from CDDFT will have anorectal manometry and rectal sensitivity tests as per local procedure using a Medtronic 3D Solid-State

High Resolution Manometry System. These tests are performed as per standard care, however rectal sensitivity testing will be performed twice more as part of non-standard care.

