7.8 Data Analysis

To investigate whether London Classification diagnoses differs when using the rectal barostat compared to elastic balloon distension, a binary indicator will be used to determine the percentage of patients who's diagnoses were in agreement. To examine this closer, a Fisher's exact test will be used to determine whether the difference in number of diagnoses between the elastic balloon distension and rectal barostat reaches a significance level of p=0.05.

To assess repeatability of sensory thresholds at first sensation, normal urge, and sustained urgency of the rectal barostat, an intraclass correlation coefficient will be calculated for each test.

To identify whether there is a correlation between total rectal capacity and the volume of the elastic balloon at the sensory threshold of sustained urgency, a Pearson's correlation will be calculated to test the strength of the relationship between these variables.

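### The design cannot determine whether the Laborie or the Medtronic balloon agrees better with the barostat, because system, site and normal range coincide

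*Protocol*

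**What the plan says.** Section 3.2 of the protocol lists as a secondary objective "To determine whether the Laborie elastic balloon test or Medtronic elastic balloon test aligns better with the rectal barostat test". Section 7.5.3 assigns one system to each site: "Participants from NUTH will have anorectal manometry and rectal sensitivity tests as per local procedure using a Laborie Solar High Resolution Manometry System" and "Participants from CDDFT will have anorectal manometry and rectal sensitivity tests as per local procedure using a Medtronic 3D Solid-State". Section 5.0 adds that "Patients identified at each site will undergo the study at the same site". Of the two systems, section 1.0 says that "they utilise different published normal ranges of sensory thresholds".

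Section 7.4 randomises the order of the tests (procedure A or B), not the balloon system. Section 7.5.4 has the barostat, which is the reference test, carried out under local procedure at both sites. Section 6.3 sets 15 participants at each site.

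Section 3.3 defines the diagnosis outcome separately for Laborie versus barostat and Medtronic versus barostat. Section 7.8 refers to elastic balloon distension without naming a system, and fixes the measure: "a binary indicator will be used to determine the percentage of patients who's diagnoses were in agreement".

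**The concern.** To say that one system aligns better is to make a claim about the device. In this study a change of device is also a change of hospital, of patients, of normal range and possibly of how the barostat is run. Nothing in the design varies one of these while holding the others fixed.

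The protocol already sees part of the difficulty. In section 2.0 it reports the service evaluation at the same two sites: "In NUTH, the majority of patients (91.4%) were diagnosed as normal, whereas in CDDFT, the majority of patients (65.7%) were diagnosed with rectal hypersensitivity". It then cautions about "the limitations such as two different cohorts of patients being studied" and about the small sample. That evaluation had 70 patients per site; this study has 15 per site, again in different patients.

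The study is meant to inform a definitive study (section 2.0) and is to be presented and published (section 12.0). A statement that one commercial system agrees better with the barostat could steer the choice of device without support from the data.

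**Working it through.** **Inputs from the protocol.** 15 participants per site (6.3); one system per site (7.5.3); no movement between sites (5.0); normal range tied to system (1.0); order of tests randomised (7.4); percentage agreement as the measure (7.8); service-evaluation shares from 70 patients per site (2.0). The protocol gives no expected agreement rate, so every agreement rate below is an assumption.

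**The plan's own figures.** 15 + 15 = 30, as stated. 64/70 = 91.4% and 46/70 = 65.7%, so the two percentages are consistent with 70 per site.

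**Can the device effect be isolated?** Take a model for agreement with an intercept and indicators for site, system and normal range. For all 30 participants the three indicators take the same value: 0 for NUTH, Laborie and the Laborie range; 1 for CDDFT, Medtronic and the Medtronic range. The matrix has 4 columns and rank 2. Only the intercept and one NUTH-versus-CDDFT contrast can be estimated. More patients under the same design would not change this.

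**Does patient mix move the measure?** Let *a* be agreement among barostat-normal patients, *b* agreement among barostat-abnormal patients, and *p* the share who are barostat-normal. Overall agreement = *a* × *p* + *b* × (1 − *p*). Use the same *a* and *b* at both sites, so that the balloons perform identically, and let *p* be 90% at one site and 35% at the other:

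- *a* = 95%, *b* = 60%: 0.855 + 0.060 = 91.5% versus 0.3325 + 0.390 = 72.25%, a gap of 19 points.
- *a* = 90%, *b* = 50%: 0.810 + 0.050 = 86.0% versus 0.315 + 0.325 = 64.0%, a gap of 22 points.
- *a* = 95%, *b* = 80%: 0.855 + 0.080 = 93.5% versus 0.3325 + 0.520 = 85.25%, a gap of 8 points.

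The spread in *p* is deliberately wide. It is close to the balloon shares in the service evaluation (91.4% normal at NUTH; 100 − 65.7 = 34.3% not hypersensitive at CDDFT), but those are not barostat shares. With a milder spread of 70% versus 50% and the first pair of rates, agreement is 84.5% versus 77.5%, a gap of 7 points.

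**How precise is the contrast?** For 80% versus 60% agreement with 15 per site, the half-width of the 95% interval for the difference is 1.96 × √(0.8 × 0.2/15 + 0.6 × 0.4/15) = 1.96 × √0.02667 = 0.32, or 32 points around an observed 20. Within a site, 12/15 (80%) has an exact 95% interval of 52% to 96%, and 10/15 (67%) one of 38% to 88%.

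**The case against.** The strongest defence is that this is a feasibility study with no primary outcome, that the comparison is one of seven secondary objectives, and that section 7.8 plans no test between systems. That stands, and it lowers the severity. It also means that low power is not the fault: exact Fisher power for 80% versus 60% at 15 per site is 11%, but nobody has proposed that test. The interval matters only because the objective speaks of determining an answer.

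A second defence is that every participant also has the barostat, so agreement is measured within patient against a reference that the service evaluation lacked. This stands in part. A reader might infer that patient mix is wholly indistinguishable from system; in fact it is nested in site and partly visible through the barostat result. Control remains incomplete, because percentage agreement still depends on mix and the barostat follows local procedure. Normal range can also fairly be regarded as part of the test as used in clinic.

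Three further inferences are tempting but unsupported:

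- *That the two systems are to be pooled.* Section 7.8 does not say so, and section 3.3 defines the outcome per system.
- *That the protocol holds the systems to classify patients very differently, or that different staff explain it.* Section 2.0 claims only a possible difference, and section 7.1 says only that the usual care team does the work.
- *That Laborie would win by chance agreement alone.* Suppose the barostat called 80% normal and 15% hypersensitive at both sites, unrelated to the balloon. Expected agreement would then be about 73–74% at NUTH and 10–37% at CDDFT. But with those shares CDDFT agreement could not exceed 15% + 34.3% = about 49% however strong the relation, while NUTH could reach 80% + 8.6% = about 89%. The example shows a difference in calibration to the barostat, not a spurious ranking.

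**Conclusion.** The concern holds in a limited form. The objective in section 3.2 cannot be answered, because system, site and normal range coincide exactly, patients are nested in site, and only test order is randomised. This follows from the protocol's text and needs no assumption about rates. The sizes do rest on assumptions: 8 to 22 points from patient mix alone under the wide spread and the agreement rates shown, and a half-width of about 32 points if agreement is 80% and 60%.

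A reader might infer that the comparison with the barostat is invalid altogether. It is not: describing agreement within each site is sound, and the sample size, test procedures and feasibility outcomes are unaffected. The fault lies in promising a ranking of devices. This should be fixed, but it does not stand in the way of the study.

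**What to change.** 1. Reword the objective in section 3.2 and in the study summary, for example: *To describe, separately for each site's balloon system, agreement with the rectal barostat; the systems will not be ranked.*
2. In section 7.8, report agreement per system, in line with section 3.3, as a full cross-table of balloon against barostat diagnoses with exact 95% intervals. Make any pooled figure secondary.
3. State that system and site are confounded, and name this as a limitation.
4. Where threshold volumes are recorded, classify each participant's balloon volumes under both published normal ranges. This shows how much disagreement comes from the cut-offs. It does not separate device from site. Sections 8.1 and 11.8.2 say only that balloon results go into the case report form, and section 3.3 names balloon volume only at sustained urgency, so confirm that all threshold volumes are captured.
5. Treat kappa as optional and do not use it to rank the systems. It also depends on prevalence: if the 64/70 normal share held, all 15 NUTH balloon diagnoses would be normal with probability (64/70)^15 = about 26%, and kappa would then be zero or undefined.

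The cost is a more modest claim and one extra tabulation, with no added patients, visits or tests. A true comparison of systems needs a design in which both are used at the same site or in the same patients.
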